*Q6	Are you satisfied with your sexual relationship even though you have fertility problems?					
For each question, check the response that is closest to your current thoughts and feelings		Always	Very Often	Quite Often	Seldom	Never
Q7	Do your fertility problems cause feelings of jealousy and resentment?					
Q8	Do you experience grief and/or feelings of loss about not being able to have a child (or more children)?					
Q9	Do you fluctuate between hope and despair because of fertility problems?					
Q10	Are you socially isolated because of fertility problems?					
*Q11	Are you and your partner affectionate with each other even though you have fertility problems?					
Q12	Do your fertility problems interfere with your day-to-day work or obligations?					
Q13	Do you feel uncomfortable attending social situations like holidays and celebrations because of your fertility problems?					
Q14	Do you feel your family can understand what you are going through?					
For each question, check the response that is closest to your current thoughts and feelings		An Extreme Amount	Very Much	A Moderate Amount	A Little	Not At All
*Q15	Have fertility problems strengthened your commitment to your partner?					
Q16	Do you feel sad and depressed about your fertility problems?					
Q17	Do your fertility problems make you inferior to people with children?					
Q18	Are you bothered by fatigue because of fertility problems?					
*Q19	Have fertility problems had a negative impact on your relationship with your partner?					
*Q20	Do you find it difficult to talk to your partner about your feelings related to infertility?					
*Q21	Are you content with your relationship even though you have fertility problems?					
Q22	Do you feel social pressure on you to have (or have more) children?					
Q23	Do your fertility problems make you angry?					
Q24	Do you feel pain and physical discomfort because of your fertility problems?					

© European Society of Human Reproduction & Embryology and American Society of Reproductive Medicine

24 Appendix H: Stop Bang Questionnaire

STOP BANG Questionnaire

Height _____ inches/cm Weight _____ lb/kg
Age _____
Male/Female
BMI _____
Collar size of shirt: S, M, L, XL, or _____ inches/cm
Neck circumference* _____ cm

1. Snoring

Do you snore loudly (louder than talking or loud enough to be heard through closed doors)?

Yes No

2. Tired

Do you often feel tired, fatigued, or sleepy during daytime?

Yes No

3. Observed

Has anyone observed you stop breathing during your sleep?

Yes No

4. Blood pressure

Do you have or are you being treated for high blood pressure?

Yes No

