1.8 Statistical Analysis

The primary analysis will use an intent-to-treat approach examining differences in the good birth outcome rate in the two treatment arms. The study is powered with 80% power and an alpha of 0.05 to detect an absolute 15% difference in good birth outcome (a live birth of an infant born at ≥ 37 weeks, with a birth weight between 2500 and 4000g and without a major congenital anomaly) between the two treatment groups. We project the proportion of good birth outcomes to be 0.25 in the standard lifestyle group and 0.40 in the intensive lifestyle group. The sample size is inflated to reflect a 20% dropout rate, giving us 190 subjects in each group. A logistic regression model will be fit to compare the treatment arms with respect to the primary outcome of good birth outcome while adjusting for the randomization stratification factors of study site and baseline BMI. The analysis of other secondary (supplemental) outcomes measured over time will entail the application of statistical methods that have been developed for correlated data since repeated observations will be made over time on each individual. For secondary outcomes such as weight loss, a linear mixed-effects model will be fit where the main independent variables will be treatment group, time, and their interaction as well as the randomization stratification factors as covariates. Logistic regression models will be used in secondary analyses to evaluate the predictive value of treatment arm, clinical site, prior exposure to ovulation induction drugs, age, and other explanatory variables on binary outcomes

(e.g., singleton live birth, abortion). Cox proportional hazards models and a Kaplan-Meier method will be applied to compare time to pregnancy in the treatment groups.

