We plan to proceed with a standardized empiric therapy for infertility after lifestyle modification that both treatment groups in this trial will receive. We plan to use our experience and data from the AMIGOS trial to power the sample size for this trial and aid in the design of the infertility treatments.

AMIGOS Preliminary Results The AMIGOS trial (Assessment of Multiple Intrauterine Gestations from Ovarian Stimulation) is a randomized trial of three empiric treatments for unexplained infertility: Clomiphene/IUI, letrozole/IUI, or human menopausal gonadotropins/IUI for up to four treatment cycles. This trial randomized 900 couples with unexplained infertility to these treatments and was completed in the last funding cycle of the RMN. We propose to adapt many of the inclusion/exclusion criteria of that study as well as some of the methodology for the empiric treatment phase. Based on the results of this trial, we have elected to use clomiphene/IUI as our empiric treatment for unexplained infertility after completion of the lifestyle modification phase. Although gonadotropin/IUI had the highest live birth rate, it also had a high rate of multiple pregnancy, including high order multiple pregnancy (triplets). Further, clomiphene/IUI had a higher cumulative live birth rate (23.3%) than letrozole/IUI (18.7%). We further extrapolated the data from the obese women (BMI \geq 30) with unexplained infertility over the first three treatment cycles in the AMIGOS trial and found that clomiphene IUI trended better both in terms of live birth and healthy live birth than letrozole (**Table 6**). We opted for three treatment cycles here to reflect current practice (i.e. to conduct 3 cycles of empiric therapy before moving on) as well as the declining pregnancy and live birth rates we experienced in the fourth treatment cycle (data not shown).

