5.1 Inclusion Criteria

1. Women ≥ 18 to ≤ 40 years of age, with one or more years infertility history, desirous of conceiving, regularly ovulating (defined as 9 or more menses per year), at initiation of participation.
2. BMI ≥ 30 kg/m² obtained at screening visit.
3. Normal uterine cavity and at least one open fallopian tube confirmed by hysterosalpingography (HSG), sonohysterography (SHG), or laparoscopy/hysteroscopy in the last three years preceding enrollment into the study. An uncomplicated intrauterine non-IVF pregnancy and uncomplicated delivery and postpartum course resulting in live birth within the last three years will also serve as sufficient evidence of a patent tube and normal uterine cavity as long as the subject did not have, during the pregnancy or subsequently, risk factors for Asherman's syndrome or tubal disease or other disorder leading to an increased suspicion for intrauterine abnormality or tubal occlusion.
4. Evidence of ovarian function/reserve as assessed by day 3 (+/-2 days) FSH ≤ 10 IU/L with Estradiol ≤ 70 pg/mL OR serum AMH ≥ 1 ng/mL within one year prior to study initiation.
5. Normal or corrected thyroid function within one year of study initiation.
6. Normal or corrected prolactin level within one year of study initiation.
7. In general good health, not taking any medications which could interfere with the study (e.g., FSH, insulin sensitizers - see Appendix for full list).
8. Ability to have inseminations following hCG administration
9. Male partner with total motile sperm in the ejaculate of at least 5 million sperm, within one year of study initiation
10. Able to have intercourse and collect semen for insemination

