5.2 Exclusion Criteria

1. Currently pregnant or successful pregnancies within 12 months of initiating participation. Clinical intrauterine miscarriages prior to initiating participation, within ASRM guidelines: subjects 35 and over must wait six months, while subjects under 35 must wait 12 months. No exclusion for biochemical pregnancies.
2. Undiagnosed abnormal uterine bleeding.
3. Suspicious ovarian mass.
4. Subjects on oral contraceptives, depo-progestins, or hormonal implants (including Implanon). A two month washout period will be required prior to screening for patients on these agents. Longer washouts may be necessary for certain depot contraceptive forms or implants, especially when the implants are still in place. A one-month washout will be required for patients who have taken oral cyclic progestins.
5. Known 21-hydroxylase deficiency or other enzyme defect causing congenital adrenal hyperplasia.
6. Type I or Type II diabetes mellitus, or if receiving antidiabetic medications.
7. Known significant anemia (Hemoglobin <10 g/dL).
8. History of deep venous thrombosis, pulmonary embolus, or cerebrovascular event.
9. Known heart disease (New York Heart Association Class II or higher).

10. Known liver disease (defined as AST or ALT >2 times normal, or total bilirubin >2.5 mg/dL).
11. Known renal disease (defined as BUN >30 mg/dL or serum creatinine > 1.4 mg/dL).
12. History of, or suspected cervical carcinoma, endometrial carcinoma or breast carcinoma.
13. History of alcohol abuse (defined as >15 drinks/week) or binge drinking of ≥ 6 drinks at one time).
14. Known Cushing's disease.
15. Known or suspected adrenal or ovarian androgen secreting tumors.
16. Allergy, known hypersensitivity or contraindication to the treatment medications used in this study including orlistat (This will include patients with chronic malabsorption syndrome or cholestasis or clomiphene (previous change in vision).
17. Couples with previous sterilization procedures (e.g. vasectomy, tubal ligation) whether or not it has been reversed.
18. Subjects with untreated poorly controlled hypertension defined as a systolic blood pressure ≥ 160 mm Hg or a diastolic ≥ 100 mm Hg obtained on two measures obtained at least 60 minutes apart.
19. Subjects who have undergone a bariatric surgery procedure in the past or are in a period of acute weight loss (defined as a weight loss of greater than 5% body weight in the last 6 months).
20. Known severe endometriosis

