This baseline visit will be performed at the start of Cycle 1 only. The initial dose of clomiphene citrate will be 100 mg/day, which may be adjusted upwards or downward depending on response in subsequent cycles. Women may undergo a total of up to 3 cycles culminating in hCG administration. Subjects may begin subsequent cycles immediately following failed cycles, as long as they meet baseline criteria of a negative urine pregnancy test. Subjects may continue in the study after one failed cycle (i.e. either no development of follicles on study medication). If a subject experiences a second failed cycle, it is recommended to discontinue the subject from the study.

1. Subject will call with menses and come in between days 1-5 of their menstrual cycle (Preferably day 3 for baseline monitoring visit).
2. Check Urine Pregnancy test.
3. Obtain weight.
4. Perform baseline ultrasound. If subject has a cyst with a mean diameter of >30mm, do not continue the visit. Have the subject return with her next menses for a repeat baseline visit.
5. Collect vaginal microbiome and rectal microbiome swab.
6. Dispense Infertility Treatment Study Medication (see Table 9). Please note, if the female has a prior history of over-response to clomiphene citrate at the 100mg dose, the starting dose may be adjusted downward.
7. Obtain central core lab specimens and blood and urine reserve (to be stored on site) for ancillary studies (with consent).

8. Dispense menstrual and intercourse diaries.
9. Schedule Day 8-12 visit for follicular monitoring.

Table 9: Study Medication and Dosing

Protocol	interval	dose	method	start	finish	future cycles
CC	Daily	100 mg	pill	Day 3*	Day 7	Can be started at 50-150 mg/d= (1 to 3 pills)

*(+/- 2 days)

Empirical treatment Cycle Visit number 2:

Within 3 days after completing 5-day drug cycle (Cycle Day 8-12)

1. Transvaginal ultrasound for endometrial and follicular monitoring.
2. Adverse effects and concomitant medications query.
3. During cycle 2 & 3, medication bottles and menstrual diaries from previous cycle will be collected.

Study treatment Cycle visits number 3 and beyond:

Visits for subjects will be conducted on an individualized basis until hCG administration. When a decision has been made to give hCG on the next day, a follow up monitoring visit on that day is unnecessary.

1. Transvaginal ultrasound examination for endometrial and follicular monitoring.
2. Adverse effects and concomitant medications query.

hCG administration day:

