10.2 Rationale for Design

Obesity is associated with subfertility through multiple mechanisms and lifestyle modification is frequently recommended as primary treatment before initiating infertility therapy. However this common sense recommendation is tempered by data that suggest that excessive or rapid weight loss as well as excessive physical activity may be associated with lower conception rates. We propose to focus on obtaining reproductive fitness through two types of lifestyle modification prior to infertility treatment. The first will be an intensive lifestyle modification designed to improve fitness through weight loss (with a dual approach of meal replacements combined with an anti-obesity medication) AND by increasing physical activity and the second arm will be a standard lifestyle modification which will focus on increasing physical activity alone. The meal replacements will be considered a prescribed medical treatment and will be dispensed and tracked to the intensive lifestyle intervention group throughout the pre-conception intervention. Both groups will be encouraged and monitored to achieve the same amount of physical activity. We hypothesize that weight loss as achieved by the more intensive intervention will be superior to the likely weight maintenance achieved with physical activity alone. However as noted in the background there are few data beyond our preliminary data to support that hypothesis. We do not have a control arm of no treatment as currently lifestyle modification is recommended universally for obese women.

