Sulfonylureas/Beta cell stimulators

acetahexamide (Dymelor)
chlorpropamide (Diabinese)
tolazamide (Tolinase)
tolbutamide (Orinase)
glimepiride (Amaryl)
glipizide (Glucotrol)
glyburide (DiaBeta Micronase)

Biguanides

metformin (Glucophage)

Incretins : GLP-1 Analogues/DPP-IV inhibitors

sitagliptin (Januvia)
vidagliptin (Glavus)
exenatide (Byetta)
liraglutide (Victoza)

Amylin Analogue

Pramlintide (Symlin)

Anti-obesity

diazoxide (Proglycem)
orlistat (Xenical)
diethylpropion (Tenuate)
phendimetrazine (Bontril)
phentermine (Adipex-P, Fastin, Ionamin)
lorcaserin (Belviq)
Phentermine/Topiramate (Osymia)

Other drugs with weight loss as a side effect

Bupropion (Wellbutrin, Zyban)
Topiramate (Topamax)
Desfenlafaxine (Pristiq)

Medications with potential longer washouts (Contact DCC)

Contraceptive Implants
Norplant (levonorgestrel implants)
Implanon
Previous clomiphene and letrozole use requires a two-month washout

Your Health and Well-Being

This survey asks for your views about your health. This information will help keep track of how you feel and how well you are able to do your usual activities. *Thank you for completing this survey!*

For each of the following questions, please mark an in the one box that best describes your answer.

1. In general, would you say your health is:

Excellent	Very good	Good	Fair	Poor
▼	▼	▼	▼	▼
 1	 2	 3	 4	 5

2. The following questions are about activities you might do during a typical day. Does your health now limit you in these activities? If so, how much?

	Yes, limited a lot	Yes, limited a little	No, not limited at all
	▼	▼	▼

a. Moderate activities, such as moving a table, pushing a vacuum cleaner, bowling, or playing golf..... 1..... 2..... 3

b. Climbing several flights of stairs 1..... 2..... 3

SF-12v2® Health Survey © 1994, 2002 Medical Outcomes Trust and QualityMetric Incorporated. All rights reserved.
 SF-12® is a registered trademark of Medical Outcomes Trust.
 (SF-12v2® Health Survey Standard, United States (English))

3. During the past 4 weeks, how much of the time have you had any of the following problems with your work or other regular daily activities as a result of your physical health?

	All of the time	Most of the time	Some of the time	A little of the time	None of the time

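### Women with earlier clomiphene or letrozole IUI cycles can enter, and that history is collected, but the primary model leaves it out

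*Combined protocol and SAP*

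**What the plan says.** **Eligibility.** Section 5.1 asks for women "with one or more years infertility history, desirous of conceiving, regularly ovulating" and says nothing about the number, type or outcome of earlier treatment cycles. In 5.2, item 16 is the only exclusion that looks at clomiphene history, and it concerns hypersensitivity, contraindication or a visual effect ("clomiphene (previous change in vision"). Appendix B adds "Previous clomiphene and letrozole use requires a two-month washout".

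**Prior users are expected.** The Cycle 1 baseline visit in 7.2 provides that "if the female has a prior history of over-response to clomiphene citrate at the 100mg dose, the starting dose may be adjusted downward".

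**Rationale.** Section 3.6 justifies three Phase II cycles by current practice ("to conduct 3 cycles of empiric therapy before moving on") and by falling pregnancy and live birth rates in the fourth AMIGOS cycle, for which no data are shown. Section 10.2 notes as background that "lifestyle modification is frequently recommended as primary treatment before initiating infertility therapy".

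**Data and analysis.** Section 7.3.1 collects infertility treatment history on case report forms. Section 1.8 lists "prior exposure to ovulation induction drugs, age, and other explanatory variables on binary outcomes" for secondary logistic models. Section 10.9 allows prior exposure to study medication as a possible covariate in the longitudinal models, and limits the primary model to treatment, recruitment site and baseline BMI. Neither description of the randomisation (10.1, 10.4.1) stratifies on prior treatment.

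**The concern.** Response to the same regimen in the past is a plausible predictor of response to it in the trial. The authors appear to agree, since they name prior exposure in their secondary models. Section 10.4.1 also states that accounting for covariates related to the outcome raises precision and power. Leaving a collected and plausibly prognostic factor out of the one model that decides the trial gives up that gain.

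There is also a question of interpretation. For a woman with three completed clomiphene/IUI cycles, study cycles 1-3 are her cycles 4-6. The primary result would pool couples at the start of therapy with couples who have already had as many cycles as section 3.6 treats as usual. The plan specifies no breakdown of the primary outcome that would separate them. The secondary models do not settle this: sections 1.8 and 10.9 describe the exposure differently, and neither defines it as a count of insemination cycles.

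**Working it through.** **1. The plan's own sample size.** Inputs (10.4.1, Table 11): 0.25 v 0.40, two-sided alpha 0.05, power 80%, dropout 20%. With pooled variance:

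n = [1.960 × √(2 × 0.325 × 0.675) + 0.8416 × √(0.25 × 0.75 + 0.40 × 0.60)]² / 0.15² = (1.298 + 0.550)² / 0.0225 ≈ 152

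152 / 0.80 = 190 per arm. Both reproduce; there is no arithmetic error here.

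**2. How far prior users could lower the Phase II rate.** The documents give neither the share f of such women nor their success rate. As an illustration, let each have the Table 6 cycle-3 good birth rate in all three study cycles, and stay within one column of Table 6.

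| | Clomiphene | All arms |
|---|---|---|
| Cumulative rate, 3 cycles | 12/70 = 17.1% | 37/241 = 15.4% |
| Cycle-3 rate | 3/59 = 5.1% | 6/196 = 3.1% |
| 1 − (1 − cycle-3 rate)³ | 14.5% | 8.9% (9.0% from the rounded 3.1%) |
| Mixture, f = 10% | 16.9% | 14.7% |
| Mixture, f = 40% | 16.1% | 12.8% |

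Mixture = cumulative − f × (cumulative − prior-user rate). The clomiphene column by cycle is 4.3%, 9.1%, 5.1%, so it shows no steady fall. The all-arms column includes letrozole (0/76 in cycle 3) and gonadotropin, which Phase II does not use. Conceptions during the 16-week lifestyle phase are not counted.

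**3. What chance imbalance could do.** With 190 per arm, the 95% limit on the between-arm difference in share is 1.96 × √(2f(1 − f)/190): 6.0 points at f = 10% and 9.9 points at f = 40%. Multiply by the gap between groups:

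- Clomiphene gap 2.7 points: shift of 0.2 to 0.3 percentage points.
- All-arms gap 6.4 points: shift of 0.4 to 0.6 percentage points.

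The target difference is 15 points, with standard error √(0.25 × 0.75/190 + 0.40 × 0.60/190) = 4.7 points.

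**4. What adjustment gains.** I simulated logistic models with and without a binary prior-user term (60,000 trials per setting, 152 per arm). Other women had rates 0.25 and 0.40; prior users had r times those rates in both arms.

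| f | r | Power, unadjusted | Power, adjusted | Gain (points) |
|---|---|---|---|---|
| 20% | 0.50 | 74.1% | 74.9% | 0.8 |
| 20% | 0.25 | 70.3% | 72.5% | 2.1 |
| 40% | 0.50 | 66.6% | 68.1% | 1.5 |
| 40% | 0.25 | 58.7% | 62.8% | 4.1 |

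Gains are taken before rounding. Keeping the odds ratio at 2.0 in both groups gives gains of 0.9, 1.9, 1.3 and 3.5 points. The Table 6 illustration implies milder ratios, 14.5/17.1 = 0.85 or 8.9/15.4 = 0.58, so on those inputs the gain would sit at or below the r = 0.50 rows.

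**The case against.** The best defence is that admitting prior users is a deliberate choice. The washout rule and the dosing note foresee them. The objective, hypothesis and primary aim (1.1, 1.2, 2.1) concern obese women with unexplained infertility, not untreated women, and the remark in 10.2 is background. Prior exposure is already collected and already in secondary models. Most of this stands. It argues against restricting entry, but does not explain why the factor is missing from the primary model.

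Four stronger readings are tempting, and the documents do not support them.

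- **The comparison is biased.** It is not. Allocation is randomised, chance imbalance is covered by the test's error rate, and step 3 shows that its likely effect is small.
- **The protocol regards further cycles as futile.** Section 3.6 cites practice and a decline in the fourth cycle only. It says nothing about cycles 5 and 6, nor about women who have since changed their lifestyle, which is the question under test.
- **Prior users pull the rate down sharply.** Setting the all-arms 9.0% against the clomiphene 17.1% would suggest so, but it mixes two columns. In addition, 3.6 says that many AMIGOS criteria will be adapted. If AMIGOS admitted prior users, its 17.1% already contains them.
- **Women with three or more cycles should be excluded.** That trades away accrual and external validity, and the documents do not show that the trade is worthwhile.

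**Conclusion.** The omission is real and worth correcting, as a matter of precision and interpretation. The plan collects a factor that it treats as explanatory elsewhere, then leaves it out of the primary model and gives no primary-outcome breakdown by it.

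The power gain is about 1-4 points if 20-40% of entrants are prior users with 0.5 to 0.25 of the planned success. The upper end needs a relative success well below what either Table 6 column suggests. Share and relative success are both assumptions. The fall in event rate in step 2 is illustrative and may already be present in the AMIGOS figures, so it does not show that 380 is too few. The case for the change rests on its very low cost.

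**What to change.** 1. In 10.9, prespecify the number of completed prior clomiphene or letrozole cycles with IUI (0, 1-2, 3 or more) as a baseline covariate in the primary logistic model, with a rule for collapsing sparse categories.
2. Tabulate it by arm with the other baseline characteristics.
3. Report the treatment effect in women with fewer than three prior cycles, labelled supportive.
4. Confirm that the case report form records the cycle count, and align the differing descriptions of prior exposure in 1.8 and 10.9.
5. Ask the sponsor to reconcile the three-cycle rationale in 3.6 with 5.1, 5.2 and Appendix B, stating which prior-treatment population is intended.

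**Cost.** Analysis-plan wording, two more model parameters, and a supportive analysis with lower power. The odds ratio becomes conditional on one more factor, so it can differ slightly from the site-and-BMI-adjusted value even without imbalance. If the form lacks the count, one field must be added. Accrual and eligibility are unaffected.
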